Comparison between the two interventions (i.e. Disease Management, the study intervention, and Usual Care, the control intervention) will be made by log-rank test, where an event is defined as hospital admission due to heart failure or death from any cause. In this analysis, the occurrence of any of these two events is defined as 'failure', and the time until the first event (hospital admission or death) will be defined as the time-to-failure. The analysis will be according to intention-to-treat, meaning that patients' data will be analysed according to their assigned intervention. The log-rank test will be one-sided at a significance level of 2.5%, where the alternative hypothesis is that this time will be longer in the study intervention group. Since the Data Monitoring Committee acts as a safety committee and the tests used for this purpose will be in the other direction, looking for poorer results in the study intervention group, no correction for multiple comparisons are needed.

Secondary analyses

There will be several secondary analyses to support the primary hypothesis. They will include:

- (i) Comparisons of baseline factors among the two study groups, e.g. age, NYHA functional classification, 6-min. walk test, left ventricular ejection fraction, type of heart failure, plasma creatinine and heart failure center;
- (ii) Adjustment for these baseline factors will be made using the Cox proportional hazards model;
- (iii) An interaction between the NYHA functional classification and study group will be tested;
- (iv) An interaction between the time of recruitment and study group will be tested, since we expect a 'learning effect' in operating the study intervention;

In addition, the two study groups will be compared for the other secondary outcomes, for example:

- (i) The number of hospital admissions for heart failure per year;
- (ii) Death from all causes;
- (iii) NYHA classification tested every 6 months during follow-up;
- (iv) Health related quality of life and depression symptoms tested every 6 months during follow-up;

Total costs will be compared between the two interventions.

The statistical methods for these comparisons will be chosen according to the distribution of each outcome (categorical, ordered or continuous). Each outcome will be tested in univariate and multiple variable models.

Potential bias and ways to reduce its effect

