***-For diabetic patients only**

****-Once a year**

Resting Echocardiographic evaluation:

Date of test: |_|_| - |_|_| - |_|_|_|_|

Echocardiographic evaluation

1. Left atrium diameter	_ _ mm
2. End-diastolic left ventricular diameter (LVEDD)	_ _ mm
3. Intra-ventricular septal thickness	_ _ mm
4. Left ventricular ejection fraction (LVEF)	_ _ %
5. Pulmonary systolic pressure	_ _ mmHg
6. Moderate or severe mitral insufficiency	1. Yes; 2. No;
7. Moderate or severe tricuspid insufficiency	1. Yes; 2. No;
8. Pressure gradient across the aortic valve	_ _ mmHg Valve surface area*: _ _ cm ² *-The pressure gradient should be calculated if greater than 25 mmHg

Six minute walk test: |_|_|_| meter. (Write '000' if not tested; specify the reason for the missing measurement: _____ |_|_|)

Resting ECG:

Date of test: |_|_| - |_|_| - |_|_|_|_|

Findings:

1. QRS width |_|_| mm

Findings (mark \checkmark where appropriate)	No	Yes
2. LBBB	_	_
3. RBBB	_	_
4. Atrial fibrillation	_	_
5. Pathological Q waves that indicate old MI	_	_

VI. Clinical evaluation summary:

1. Is there evidence for high-output heart failure? 1. Yes; 2. No

2. Does the patient have chronic atrial fibrillation? 1. Yes; 2. No

3. Characteristics of the heart failure:

a. Mainly left heart failure; (no or minimal right heart failure);

b. Mainly right heart failure; (no or minimal left heart failure);

c. Combined left and right heart failure;

4. Does the patient have an implantable device?

a. **VVI** pacemaker;

b. Atrial-ventricular pacemaker; **DDD**

c. Biventricular pacemaker; **CRT**

d. Biventricular pacemaker and defibrillator (**CRTD**)

e. Defibrillator without pacing (**ICD**)

f. No defibrillator or pacemaker

5. Recommended medical treatment (treatment plan delivered to the primary practitioner):

Drug	Dose	ATC code
1.	□□□ mg/gr/units X □□/day	□□□□□
2.	□□□ mg/gr/units X □□/day	□□□□□
3.	□□□ mg/gr/units X □□/day	□□□□□
4.	□□□ mg/gr/units X □□/day	□□□□□
5.	□□□ mg/gr/units X □□/day	□□□□□
6.	□□□ mg/gr/units X □□/day	□□□□□
7.	□□□ mg/gr/units X □□/day	□□□□□
8.	□□□ mg/gr/units X □□/day	□□□□□
9.	□□□ mg/gr/units X □□/day	□□□□□

VII. Study eligibility check

Inclusion criteria:

I. For patients discharged from hospital up to two months before assessment for study enrolment:

1. Age 18 years or older
2. The patient was hospitalized for:
 - a. newly diagnosed, acute heart failure, or
 - b. exacerbation of chronic heart failure, or

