7 EFFICACY ANALYSIS

7.1 Primary analysis of primary endpoint

The analyses to be conducted at the final statistical analysis are described in this Section. The primary endpoint is time to the combined outcome (mortality or hospitalization due to heart failure, whichever happens first). The Cox regression model will be used to compare the treatment groups with respect to this outcome, and the comparison will be adjusted for the following baseline factors: sex, age (5 categories: <50, 50-59, 60-69, 70-79, 80+), center, and functional impairment (NYHA class) at baseline.

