7.2 Secondary analyses

7.2.1 Secondary Analyses of the Primary Endpoint

All analyses will be adjusted for the same baseline factors as mentioned in 7.1 plus others that are unbalanced between the treatment groups, i.e are significantly different at the 10% significance level when entered separately. The additional baseline factors that will be considered are:

- A. 6-minute walk test
 - B. Recruited after hospitalization or from the community
 - C. Year of recruitment
 - D. Underlying cause of heart failure: ischemic/non-ischemic
 - E. Type of heart failure (left ventricular ejection fraction (LVEF) %): preserved (LVEF (%) \geq 50%)/ non-preserved (LVEF%)<50%.
 - F. Co-morbidity: diabetic/ non-diabetic
 - G. Adherence to HF medication
1. The principal statistical analysis mentioned in 7.1 with additional adjustment.
 2. Cox regression for the outcome mortality from any cause.
 3. Cox regression with the outcome re-hospitalization due to heart failure.

For each of these outcome models, the following interactions will be tested:

- i. Between arm and year of recruitment
- ii. Between arm and center
- iii. Between arm and recruitment after hospitalization or from the community
- iv. Between arm and underlying cause of HF (ischemic/ non-ischemic)
- v. Between arm and type of HF (preserved (LVEF \geq 50%)/ non-preserved (LVEF<50%))
- vi. Between arm and co-morbidity (diabetic/ non-diabetic)
- vii. For outcomes (1)-(3) above, we will investigate the interaction between treatment arm and time from entry to the trial. This is equivalent to testing the assumption

that the hazards in the two treatment arms are proportional over time – what is known as the proportional hazard assumption.

7.2.2 Analyses of Secondary Endpoints (events are counted until 31/7/12, ignoring early termination)

Fourteen secondary end-points will be analyzed to provide insight into the benefits of the disease management program. The analyses will be conducted on the ITT dataset. All the analyses will be adjusted for the following baseline factors:

- A. Sex
- B. Age (in five groups, as above)
- C. Center
- D. Functional impairment (NYHA) at baseline

- 1. Cox regression with mortality due to any cause.
- 2. Cox regression with re- hospitalization due to HF
- 3. Regression with total days of hospitalization and total number of hospital admissions due to HF
- 4. Regression with total days of hospitalization and total number of hospital admissions due to acute exacerbation

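### SAP 7.2.1 uses LVEF only as a 50% split and leaves out baseline creatinine; adding continuous LVEF beside the split, and creatinine to the adjusted models, is a minor but nearly free improvement

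*Supplement*

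**What the plan says.** - **SAP 7.1** adjusts the primary Cox model for sex, age group, "center, and functional impairment (NYHA class) at baseline". It contains neither LVEF nor creatinine.
- **SAP 7.2.1, factor E** is "Type of heart failure (left ventricular ejection fraction (LVEF) %): preserved" (50% or above) against non-preserved (below 50%). Factors A to G join the 7.1 covariates only if they are "significantly different at the 10% significance level when entered separately" between the arms.
- **SAP 7.2.1, interaction (v)** uses the same two classes. It is run for the combined outcome, death and heart failure re-hospitalization.
- **Creatinine** appears in none of the covariate lists in 7.1, 7.2.1 or 7.2.2, and no reason is given.
- **Protocol, Statistical analysis, Secondary analyses (i)** gives example baseline factors that include "left ventricular ejection fraction, type of heart failure, plasma creatinine and heart failure center". Item (ii) continues: "Adjustment for these baseline factors will be made using the Cox proportional hazards model". It states no coding and no imbalance condition.
- **Protocol items (iii) and (iv)** plan two arm interactions. The first reads "An interaction between the NYHA functional classification and study group will be tested"; the second concerns time of recruitment. The LVEF interaction first appears in the SAP.
- **Protocol Appendix C** records LVEF in percent and creatinine in mg/dL.

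**The concern.** With a single cut at 50%, patients with an LVEF of 15% and of 49% are treated as identical. Two things follow for LVEF:

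- Interaction (v) is the SAP's only test of whether benefit depends on LVEF. A gradual change contributes to it only through the difference between two class averages. A null result from such a test is weak evidence of equal benefit across the LVEF range.
- As an adjuster, an imbalance between the arms that lies wholly below 50% leaves the class shares equal. It therefore cannot trigger entry of factor E.

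Creatinine is a separate matter. It is collected at baseline and the protocol treated it as a factor for adjustment, but no SAP model can use it. In a Cox model, omitting a prognostic covariate costs some power and pulls the estimated hazard ratio toward 1.

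**Working it through.** **The plan's own figures.** The documents give no power or information figure for any interaction test. The nearest stated figure is re-hospitalization power, which shows that the planning arithmetic is sound. A 33% control rate with an odds ratio of 0.67 gives 24.8% in the intervention arm, and a two-sided 5% test has 88.0% power at 600+600 and 84.3% at 400+800 (stated: 89% and 85%). This has no bearing on the LVEF question.

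**Information kept by the split, linear effect, normal LVEF.** Let q be the share with LVEF at or above 50%, z the normal quantile for q, and φ the normal density. The split test keeps, relative to a test on the continuous value,

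E = φ(z)² / [q(1 − q)].

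The documents do not give q, so a range is shown.

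| Assumed q | E |
|---|---|
| 10% | 34% |
| 15% | 43% |
| 20% | 49% |
| 30% | 58% |
| 40% | 62% |
| 50% | 64% |

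At q = 15%, for example, z = 1.036 and φ = 0.233, so E = 0.0544 / 0.1275 = 0.43.

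**In terms of power.** If the continuous test had 80% power, the split test would have Φ(2.80√E − 1.96). That is 45% at E = 0.43 and 60% at E = 0.62.

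**Check by simulation.** Cox models were simulated with 1,360 patients, 1:1 allocation, an assumed hazard of 0.3 per year, censoring spread over 1 to 5 years, and an assumed linear interaction of 0.18 in the log hazard ratio per SD of LVEF. Information kept is the squared ratio of mean z-statistics:

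- 15% preserved: (1.664 / 2.520)² = 0.436; power 70% continuous, 40% split.
- 40% preserved: (1.967 / 2.492)² = 0.623; power 66% continuous, 48% split.

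**Other LVEF shapes, effect still linear.** Information kept is the squared correlation of LVEF with the 50% indicator.

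- Uniform from 15% to 65% (30% preserved): 63%.
- Bimodal, with means of 30% and 58% and 15-40% of patients in the upper component: 64-78%.
- Right-skewed with 12% preserved: 54%.

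**Effect that steps at 50%.** With an assumed jump of 0.45 in the log hazard ratio, the ranking reverses. The split carries (2.307 / 1.581)² = 2.1 times the information of the linear test at 15% preserved, and (3.144 / 2.562)² = 1.5 times at 40%.

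**Creatinine.** Simulated power for the treatment effect, without and with a covariate of the assumed strength per SD:

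- Hazard ratio 1.2: 83.3% and 83.7% (+0.4 points).
- Hazard ratio 1.3: 74.6% and 76.7% (+2.1 points).
- Hazard ratio 1.5: 74.1% and 80.1% (+6.0 points).

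These gains assume that the covariate is always in the model. Under the 10% rule in 7.2.1, a factor in a randomized trial passes the screen about one time in ten, so merely listing creatinine would rarely deliver them.

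**The case against.** The case for leaving 7.2.1 as it stands has real weight.

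- *Preserved and non-preserved are named disease types.* Asking whether the programme works alike in both is a legitimate prespecified question, and the two-class test is the stronger one if the effect steps at 50%. This stands. It argues for keeping the split and adding to it; replacing the split would be a trade-off.
- *The protocol list is illustrative.* It is introduced as examples, and the Summary of Changes calls the protocol's section preliminary, with the SAP finalized before data analysis. This also stands. A reader might infer that the SAP breaches the protocol, but a later plan that narrows a list of examples is no fault in itself. The point rests on the value of using data already collected.
- *The information loss is not a known property of this trial.* A reader might take 43-62% as a fact about interaction (v). The documents give neither the preserved share, nor the LVEF distribution, nor the shape of any effect, so the figure is conditional.
- *Creatinine and the LVEF interaction are unrelated.* A reader might infer that dropping creatinine weakens interaction (v). It takes no information from that test.

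The objection does not explain why a measured percentage should be used only in two classes, or why creatinine was left out.

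**Conclusion.** The point holds as a minor one, in two separate parts.

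1. **LVEF.** If benefit changes gradually with LVEF, interaction (v) works with a fraction of the available information. With a linear effect that fraction is about 43-62% for a normal LVEF with 15-40% preserved, 34% with 10% preserved, and about 63-78% for uniform or bimodal shapes. All of these inputs are assumptions. If the effect steps at 50%, nothing is lost and the split is preferable.
2. **Creatinine.** Its absence forgoes a small gain in the secondary adjusted models, from negligible at a hazard ratio of 1.2 per SD to about 6 power points at 1.5.

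It is tempting to extend the power loss and the attenuated hazard ratio to the trial's main result. The documents do not support that: the point concerns only 7.2.1, and the primary comparison in 7.1 has its own fixed covariates.

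**What to change.** In SAP 7.2.1:

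- Enter LVEF as a continuous value (linear or spline, chosen in advance) and baseline creatinine (scale chosen in advance) in the additionally adjusted models, whatever the result of the 10% imbalance test. If creatinine is to stay out, state why.
- Keep the prespecified preserved/non-preserved interaction (v) and its subgroup hazard ratios.
- Add an arm-by-continuous-LVEF interaction, labelled as a supporting test, for each of the three outcomes.

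The cost is a few lines of SAP text and code and a few more model terms. Both values are already collected, and gaps fall under the multiple imputation in SAP section 2. The downside is one more secondary interaction test per outcome: 7 × 3 = 21 tests become 8 × 3 = 24, which should be borne in mind when any single one is read.

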1.9 Baseline Assessment and Follow-up Visits at the Heart Failure Centers

Baseline evaluation includes a cardiologist-completed questionnaire on eligibility criteria, medical conditions underlying heart disease; cardiovascular risk factors; and other clinical information related to the patients' heart failure (e.g. presence of arrhythmia, implanted pacemaker or ICD).

- I. Nurse-completed questionnaire on chronic medical therapy.

- II. Nurse-supervised 6-minute walk test.
- III. PHQ-9 and SF-36 questionnaires completed by the patient.
- IV. BNP on-site assessment (starting from 2009).

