- 5. Regression with total days of hospitalization and total number of hospital admissions due to HF complications (including HF treatment adverse effects)
- 6. Regression with total days of hospitalization and number of hospital admissions for any cause
- 7. Functional impairment (NYHA class) at 6 month intervals
- 8. 6-minute walk test at 6 month intervals (in whole meters including zeros, probably will be categorized).

The 8th and 9th secondary endpoints are ordered outcomes. Therefore the proportional odds model using the GEE method implemented in the Genmod procedure (SAS 9.2), with repeated measurements, will be fitted. The proportional odds assumption will be tested and if violated a partial proportional odds model will be fitted.

- 9. Quality of life
SF36 at 6 month intervals – (score in 2 major domains (physical, mental)) – the GEE method implemented in the Genmod procedure (SAS 9.2), with repeated statement, will be fitted. If the data appear continuous then we will use GEE for a continuous outcome; if there are clumps of measurements (at 0 or 100 say), then we will categorize the data and use the proportional odds model version of GEE.
- 10. Regression model with repeated measures for Depression (PhQ9) at 6 month intervals adjusted for baseline value (subgroup with baseline value)
- 11. Regression model with repeated measures for BNP since 2009 at 6 month intervals, adjusted for baseline value (subgroup with baseline value).
- 12. Adherence to guidelines for recommended medical treatment. Two types of medical treatments will be considered: ACE-I/ARB's and Beta-blockers. We will examine adherence to each individual type and to their combination. Adherence to their combination will be scored 0,1 or 2 for patients who do not take any of the two types, patients taking only one type and patients taking both types of medicine, respectively. The two arms will be compared at 6 month intervals for their adherence to medical treatment using the proportional odds model or the partial proportional odds model using the Genmod procedure (SAS 9.2) with repeated statement.

Statistical Analysis Plan

13. A separate analysis will be conducted on the total cost for health care provider to all health care services supplied to the disease management program (not including cost of disease management manpower and infrastructure designated for the study disease program).

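### The models for 6-minute walk, SF-36 and medication adherence leave out each outcome's own baseline value, which is collected and whose counterpart is used for PHQ-9 and BNP

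*Supplement*

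**What the plan says.** SAP 7.2.2 sets one covariate list for the secondary endpoints: "All the analyses will be adjusted for the following baseline factors", followed by sex, age in five groups, center and "Functional impairment (NYHA) at baseline". The individual items then differ.

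- Item 8, walk test: "6-minute walk test at 6 month intervals (in whole meters including zeros, probably will be categorized"). It is modelled as an ordered outcome by proportional-odds GEE. No baseline walk term is named.
- Item 9, SF-36 physical and mental scores: "the GEE method implemented in the Genmod procedure (SAS 9.2), with repeated statement, will be fitted". The form is left open: "If the data appear continuous then we will use GEE for a continuous outcome", and otherwise the scores are categorized. No baseline score is named.
- Item 12, adherence scored 0, 1 or 2: "The two arms will be compared at 6 month intervals for their adherence to medical treatment using the proportional odds model" or a partial version of it. No baseline adherence term is named.
- Item 10: "Regression model with repeated measures for Depression (PhQ9) at 6 month intervals adjusted for baseline value (subgroup with baseline value"). Item 11 (BNP) has the same baseline adjustment.

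The endpoint list in SAP 4.2 makes the same distinction, naming baseline adjustment for endpoints 10 and 11 only. SAP 1.9 schedules the walk test, a nurse questionnaire on chronic medication, and "PHQ-9 and SF-36 questionnaires completed by the patient" at baseline. SAP 1.10 says baseline visits were held for all randomized patients.

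**The concern.** A patient's own starting value is often a strong predictor of later values of the same score. Leaving it out puts explainable variation into the residual and lets any chance difference between arms at baseline carry into the follow-up comparison. The SAP gives no reason for treating SF-36 differently from PHQ-9, though patients complete both at the same visits.

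Quality of life and functional status are both named in the protocol's study hypotheses, so a needless loss of power there matters more than for a purely descriptive endpoint. Adherence is not among those hypotheses.

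SAP 7.2.1 does list baseline walk distance and adherence to heart failure medication as candidate covariates. That applies only to the Cox models there, and only if the factor is unbalanced at the 10% level. It does not carry over to 7.2.2.

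**Working it through.** **Plan's own figure.** There is none to reproduce. The protocol's power calculations concern mortality and re-hospitalization. No standard deviation, correlation or effect size is given for walk distance, SF-36 or adherence.

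**Which models lack their own baseline**

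| Item | Outcome | Baseline collected | Own baseline in model |
|---|---|---|---|
| 7 | NYHA | yes | yes, through the common list |
| 8 | 6-minute walk | yes | no |
| 9 | SF-36 | yes | no |
| 10 | PHQ-9 | yes | yes |
| 11 | BNP | from 2009 | yes |
| 12 | Adherence | yes, via the medication questionnaire | no |

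**Inputs.** 1,361 randomized less one excluded gives 1,360 (SAP 1.11). At 1:1 (SAP 1.5) that is about 680 per arm. The test is two-sided at 5% (SAP 5.2). Assumed: ρ, the correlation of baseline with follow-up given the listed covariates, from 0.3 to 0.7; and an effect of 0.15 SD for illustration. Using 680 per arm supposes that every patient contributes, so absolute power is a best case. The variance ratios do not depend on it.

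**Continuous score, one visit.** Residual variance ratio = 1 − ρ²; SE ratio = √(1 − ρ²). Effect detectable at 80% power without baseline = (1.960 + 0.842) × √(2/680) = 0.152 SD; with baseline, multiply by the SE ratio.

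| ρ | Variance ratio | SE reduction | Detectable effect (SD) | Power for 0.15 SD |
|---|---|---|---|---|
| not adjusted | 1.00 | – | 0.152 | 79% |
| 0.3 | 0.91 | 4.6% | 0.145 | 83% |
| 0.5 | 0.75 | 13.4% | 0.132 | 89% |
| 0.7 | 0.51 | 28.6% | 0.108 | 97% |

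**Continuous score, mean of four visits**, equal correlation ρ between all occasions. With v = (1 + 3ρ)/4, the ratio is (v − ρ²)/v:

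- ρ = 0.3: (0.475 − 0.09)/0.475 = 0.81
- ρ = 0.5: (0.625 − 0.25)/0.625 = 0.60
- ρ = 0.7: (0.775 − 0.49)/0.775 = 0.37

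**Chance imbalance.** The SE of a baseline difference is √(2/680) = 0.054 SD, so 95% of such differences lie within 1.96 × 0.054 = 0.106 SD. At ρ = 0.5 about half of that, 0.053 SD, carries into follow-up. This is the same loss seen from another side: ρ² × 2/680 is exactly the variance that adjustment removes.

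**Ordered outcome.** Simulation of a five-category proportional-odds model at one visit: 1,360 patients, a latent shift of 0.15 SD, a binary NYHA-like covariate already in the model, 300 replicates per setting. Here ρ is the latent correlation before the NYHA-like term is taken out.

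| ρ | Power without baseline | Power with baseline |
|---|---|---|
| 0.3 | 77% | 78% |
| 0.5 | 76% | 82% |
| 0.7 | 77% | 94% |

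The simulation error of a single power figure is about √(0.77 × 0.23/300) = 2.4 points, so the gain at 0.3 is negligible. The three-level adherence score was not simulated separately.

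**The case against.** The best defense is that these are supportive secondary endpoints, that randomization already prevents bias, and that baseline NYHA, age, sex and center are in every model. NYHA will absorb part of what baseline walk distance could explain, and plausibly part of the SF-36 physical score. If the partial correlation is only 0.3, the single-visit variance saving is 9%. All of this stands and limits the size of the point. It does not explain why two outcomes get their own baseline and three do not. One could also suppose that the month-0 value enters the GEE as a repeated response, but the SAP does not say so.

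Some stronger readings are tempting, and the documents do not support them.

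- *The 1 − ρ² savings apply to all three outcomes.* They hold for a linear model of a continuous score. Walk and adherence are planned as proportional-odds models, and SF-36 may be. There, adjustment moves the conditional odds ratio away from 1 and raises power; it does not shrink the standard error.
- *GEE is unsuitable because mortality is high, so a mixed model is needed.* A mixed model valid under missing-at-random does not resolve scores that do not exist because the patient has died. The protocol's 18% is an assumption for usual-care patients in the first 12 months, not a yearly rate for both arms. GEE versus a mixed model is a trade-off, not an error.
- *Limiting items 10 and 11 to patients with a baseline value contradicts SAP sections 2 and 6.* Section 2 promises imputation only so far as it is feasible, and section 6 defines intention-to-treat by keeping patients in their allocated arm. For BNP the subset is largely structural, since testing began in January 2009. For PHQ-9 one may fairly ask why imputation is not used, but that is no contradiction.

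**Conclusion.** The omission is in the text, appears in both SAP 4.2 and 7.2.2, and is unexplained. It costs efficiency and leaves chance imbalance uncorrected in three secondary endpoints. It is not a bias, and it has no bearing on the primary analysis.

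The size cannot be fixed from the documents. Under assumed partial correlations of 0.3, 0.5 and 0.7, a continuous SF-36 score would gain 9%, 25% and 49% in single-visit residual variance. For the ordered outcomes the gain is in power: negligible at 0.3, moderate at 0.5, and substantial only at 0.7. It would be zero only if baseline predicted nothing beyond the four listed covariates. A worthwhile improvement, not a flaw that undermines the trial.

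**What to change.** In SAP 7.2.2:

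1. Add baseline 6-minute walk to model 8, the matching baseline SF-36 physical or mental score to model 9, and the baseline adherence score (0, 1 or 2) to model 12.
2. State that missing baselines in these models are handled by the multiple imputation already named in section 2, so that no patient is dropped for lack of one.
3. State that 000 on the walk-test form, which Appendix C of the protocol uses for a test not done, is treated as missing in the baseline covariate and not as 0 metres. This needs saying because item 8 expects zeros in the data.
4. Note that odds ratios from the ordered models are then conditional on baseline as well as on the listed factors.

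The cost is a few lines of SAP text, one covariate per model, a baseline imputation step and a check of the walk coding. The estimation method stays as planned and no new data are collected.
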